## **6.3. Other statistical analyses that will be conducted**

Pearson correlations (or Spearman rank correlation for non-normally distributed variables) between changes in serum fatty acids (presented as % of all fatty acids in that lipid compartment) and changes in liver fat content (%) and changes in HbA1c (mmol/mol) will be performed.

Pearson correlations (or Spearman rank correlation for non-normally distributed variables) between changes in liver fat content (%) and changes in HbA1c (mmol/mol), HOMA-IR, fasting plasma glucose (mmol/L), fasting serum insulin (mU/L), pancreatic fat (%), LDL-cholesterol (mmol/L), HDL-cholesterol (mmol/L), triglycerides (mmol/L), apoB (g/L) and apoA1 (g/L) will be performed.

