## 1. Introduction

Randomized controlled studies investigating the impact of replacing dietary carbohydrates with polyunsaturated fat (PUFA) on liver fat content and cardiometabolic risk in individuals with prediabetes and T2D are lacking. Also, the effects of a Healthy Nordic Diet on liver fat content and glycemic control have not been investigated. This study therefore aims to:

- Investigate the effects of the diets on liver fat content (primary aim)
- Investigate the effects of the diets on pancreatic fat, visceral fat, lean tissue, glycemic and lipid control
- Investigate the effects of the diets on plasma markers of de novo lipogenesis (DNL) and desaturation (i.e. stearoyl-Coenzyme desaturase 1, SCD-1) as well as on hepatic DNL using MRI spectroscopy
- Investigate gene-diet interactions, especially if common gene variants (e.g. in PNPLA3) known to increase liver fat and dyslipidemia, may modify the dietary effects.
- Perform lipidomic analyses to identify potential mechanistic pathways that may associate with diet-induced changes in liver fat, pancreatic fat, visceral fat, insulin sensitivity, dyslipidemia or DNL

Our hypothesis is that a customized diet will effectively reduce liver fat through suppression of hepatic DNL and SCD-1 activity, and thereby improve atherogenic dyslipidemia, insulin resistance and hyperglycemia in individuals with prediabetes and T2D.

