### **Exclusion criteria**

- BMI  $>$ 40
- Alcohol intake  $>$ 20 g/day
- Unwillingness to follow a new prescribed diet for 1 year
- Diet-induced weight loss ( $\geq$ 10%) the preceding 3 months of screening
- Malignant disease
- Severe kidney and liver disease
- Heart failure or other severe CVD
- Claustrophobia or metal parts in the body (MRI)

Subjects enrolled in this study will be allocated to three different diet groups in a 1:1:1 allocation ratio using stratified randomization with type-2 diabetes status (yes/no) and gender (male/female) as stratifying factors. Subjects will be followed prospectively for 12 months.

The three diet-groups are:

**Experimental:** Customized diet to reduce liver fat

Ad libitum diet high in plant-derived PUFA and lower in carbohydrates

**Experimental:** Healthy Nordic diet

Ad libitum diet, based on Nordic foods, higher in carbohydrates (high fiber/low GI) and lower in fat but rich in monounsaturated fatty acids (MUFA) and PUFA

**Active Comparator:** Control

Ad libitum diet in accordance with the Nordic Nutrition Recommendations

Further details of each diet can be found in the study protocol registered at ClinicalTrials.gov (NCT04527965).

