## **2.1. Sample size calculation**

The sample size calculation was based on Lehr's formula for comparison between two groups, assuming equal treatment effects for the two experimental diets. The standard deviation (SD) of the change in liver fat was 1.95 and 2.42 in two of our previous trials (1,2). As the population in the NAFLD trial will differ (e.g. higher prevalence of type 2 diabetes) compared to these other trials, we assume a SD of 3 for the current calculation. Given that 5% liver fat is the cut-off for NAFLD, we considered a 2% difference between groups as clinically relevant. To detect a difference of 2%-points in liver fat between the control group and one experimental group, n=36 individuals per group are needed with  $\beta=0.80$  and  $\alpha=0.05$ . To allow for 25% drop-out, n=50 individuals per group will be included. Thus, a total of n=150 individuals will be randomized.

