### 6.1. Primary outcome

For the primary outcome a General Linear Model (GLM) will be applied using  $\Delta$ liver fat (%) between month 12 and baseline as the dependent variable, treatment group as factor and type-2 diabetes status (yes/no), gender (male/female) and baseline liver fat content (%) as included covariates. The GLM will be applied for the ITT-population (defined above) as well as for the PP-population (defined above). Independent samples post-hoc t-tests will follow if between-group statistical significance is observed.

A sensitivity analysis will be conducted for the primary outcome in both the ITT- and PP-population, with weight change included as an additional covariate in the GLM.

Treatment effects will be presented as mean or median differences (%) with 95% confidence intervals and with corresponding p-values.

When assumptions of the GLM are not satisfied, the Willett's residual method will be applied, followed by Mann-Whitney U post-hoc tests.

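### Section 6.3 gives the change-on-change correlations no term for diet arm, so on its plain reading differences between arm means alone can produce a correlation

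*SAP*

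**What the plan says.** SAP section 6.3 has two sets of analyses. The first is "Pearson correlations (or Spearman rank correlation for non-normally distributed variables) between changes in serum fatty acids" on one side and changes in liver fat and HbA1c on the other. The second is "between changes in liver fat content (%) and changes in HbA1c (mmol/mol), HOMA-IR, fasting plasma glucose (mmol/L"), continuing to a total of ten markers. Neither set mentions diet arm, a partial correlation or analysis by arm. The section also does not say which analysis population is used, or whether the arms are pooled.

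Section 6.1 does spell out its adjustment: the primary model has "treatment group as factor and type-2 diabetes status (yes/no), gender (male/female) and baseline liver fat content (%) as included covariates".

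Three other places bear on how arm relates to these variables:

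- The diet-group description in section 2 has participants "allocated to three different diet groups in a 1:1:1 allocation ratio". One diet is an "Ad libitum diet high in plant-derived PUFA and lower in carbohydrates". The Nordic diet is also defined partly by its fat composition.
- Section 5.2 uses changes in linoleic acid, DHA and palmitoleic acid as examples of markers that separate high from low compliers. It therefore treats these fatty acids as indicators of what was eaten.
- Section 2.1 sizes the trial for a 2 %-point difference in liver fat with an SD of 3, "assuming equal treatment effects for the two experimental diets". Section 1 states the hypothesis that "a customized diet will effectively reduce liver fat through suppression of hepatic DNL and SCD-1 activity".

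**The concern.** Randomised diet is a common cause of both changes. Circulating fatty acids should differ by arm because the diets differ in fat, whatever happens in the liver. If a diet also lowers liver fat, the three arm means line up and pull the pooled correlation away from zero, even when fatty-acid change says nothing about liver-fat change among participants on the same diet.

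In that case the correlation largely restates the treatment effect. A pooled coefficient with p<0.05 could still be taken as separate evidence that the two changes go together, and so as support for the hypothesis in section 1. A pooled correlation cannot tell these explanations apart. An arm-adjusted one can at least show whether any association remains once the arm means are removed.

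**Working it through.** **Inputs from the SAP.** Three arms, 1:1:1. Liver-fat difference 2 %-points, SD 3, power 0.80, alpha 0.05, 36 evaluable and 50 randomised per arm, 25% drop-out (sections 2, 2.1 and 6). Two-sided testing is assumed.

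**The plan's own figure.** Lehr's formula gives 16 × (3/2)² = 36 per group, as stated. Allowing for drop-out, 36/0.75 = 48, against 50 planned. The sample size reproduces. It serves here only to fix the liver-fat shift, d = 2/3 = 0.667 SD, and the numbers analysed: 3 × 36 = 108 completers, or 150 if everyone is included.

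**Assumption not in the SAP.** The diet shift in the fatty acid, f, in within-arm SD units, is varied from 0.25 to 2.0. It is taken as a rise; a fall reverses the sign of r.

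**Pooled correlation when the within-arm correlation is 0.**

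r = cov(arm means) / √[(1 + var of liver-fat means)(1 + var of fatty-acid means)]

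If both experimental diets shift both variables, the liver-fat means are (0, −d, −d) and the fatty-acid means are (0, f, f). Then:

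- var of liver-fat means = (2/9)d² = 0.099
- var of fatty-acid means = (2/9)f²
- cov = −(2/9)df

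For f = 1: r = −0.148 / √(1.099 × 1.222) = −0.128.

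If both diets lower liver fat but only one shifts the fatty acid, the fatty-acid means are (0, f, 0). The covariance is then −df/9, and r is half as large.

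**How often p<0.05.** From 20,000 simulated trials per row, with normal data, Pearson correlation and zero within-arm correlation:

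| Fatty-acid shift (SD) | r, both diets shift both | p<0.05, N=108 | p<0.05, N=150 | r, one diet alone shifts the fatty acid | p<0.05, N=108 | p<0.05, N=150 |
|---|---|---|---|---|---|---|
| 0.25 | −0.035 | 6% | 7% | −0.018 | 5% | 6% |
| 0.5 | −0.069 | 11% | 13% | −0.034 | 7% | 7% |
| 1.0 | −0.128 | 27% | 35% | −0.064 | 10% | 12% |
| 1.5 | −0.173 | 44% | 57% | −0.087 | 14% | 19% |
| 2.0 | −0.206 | 58% | 72% | −0.103 | 18% | 24% |

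A separate simulation with 37 per arm (111 completers) and shifts of 0.5, 1.0 and 1.5 SD gave 11%, 27% and 45%.

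**Other patterns.** If one diet alone shifts both variables, the results match the columns for both diets. If no diet shifts liver fat, r is 0 and the rejection rate stays near 5%.

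**After adjustment for arm.** Correlating residuals from the arm means, with two fewer degrees of freedom, gives a mean r of 0.00 and p<0.05 in 4.7% to 5.3% of trials in every scenario.

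**Not computed.** The Spearman version was not simulated. No size is claimed for the ten markers in the second set. The same formula applies to them, but their shifts by arm would be further assumptions.

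**The case against.** **Silence on pooling.** Section 6.3 does not state that the arms are pooled, and by-arm reporting is not excluded. This stands as a limit. Pooling is still the plain reading, because section 6.1 names its adjustment terms and section 6.3 names none. If by-arm analysis is intended, the section needs to say so.

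**Adjustment answers a different question.** Under the section 1 hypothesis, diet acts on liver fat through lipogenesis, so variation between arms may be part of the true signal. Removing it leaves variation within arms, which can itself be confounded, for example by adherence or weight change. This also stands. A reader might infer that the pooled correlations are invalid and should be replaced; that goes too far, because they are a fair description of the whole sample. Nor would the adjusted version show a link within persons: each participant supplies one change per variable, so it is an association between participants within arms.

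**The link to mechanism.** A reader might infer that section 6.3 is how the plan means to establish mechanism, because section 1 aims to "identify potential mechanistic pathways that may associate with diet-induced changes in liver fat". The document does not support this. That aim concerns the lipidomic analyses, and section 6.3 itself claims no mechanism. The hypothesis sentence in section 1 shows only why such a reading may follow.

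**Size.** The fatty-acid shifts are assumed. The 2 %-point difference is the one judged clinically relevant for sizing, not a forecast. The induced r is small: 0.17² is about 3% of variance. All of this is correct and limits the point, but does not remove it.

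**Extra covariates.** Nothing in the argument or the calculation calls for adding diabetes status or gender to these correlations.

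**Conclusion.** The point holds as a minor, inexpensive improvement to an ancillary analysis. As written, section 6.3 allows a correlation to arise from arm means alone.

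At the plan's own liver-fat difference, with zero within-arm correlation and both diets shifting both variables, fatty-acid shifts of 0.5 to 1.5 SD raise the chance of p<0.05 from 5% to about 11% to 45% with about 110 completers. The result depends on pooling, on the assumed fatty-acid shift and on which arms shift. Inflation is slight to moderate when only one of two effective diets moves the fatty acid, and absent when liver fat does not move.

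A reader might infer that the trial's main conclusions are at risk. They are not: the primary and secondary treatment comparisons do not use these correlations.

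**What to change.** In section 6.3, for both sets of correlations:

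- State whether the arms are pooled.
- Report correlations adjusted for randomised arm (partial Pearson, or partial Spearman on ranks) beside the pooled values.
- Label the pooled values descriptive.
- Base any statement about an association beyond the diet effect on the arm-adjusted values.

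The cost is a few lines of SAP text and two degrees of freedom; no new data are needed. The adjusted correlations may be smaller, and they leave out any part of the association that acts through the contrast between diets. That is the reason to keep the pooled values alongside.

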## **7. Missing data**

Missing numerical and categorical data (including both dependent- and explanatory variables) will be imputed using the technique of multiple imputation by chained equations (MICE). Categorical data will be coded into dummy variables. Number of missing values for each variable of which have been imputed will be presented as n/% for each group separately and in total.

